4 STUDY DESIGN

4.1 Overall Design

The study will select a total of around 30 Tier 2 and Tier 3 hospitals across China and enrol approximately 1500 asthma patients ≥ 14 years old with all severities from the 30 participating hospitals. To represent the real-world situation of patients, pulmonologists and treatment practice, hospital selection will include as many as provinces or municipalities in mainland China, where the altitude is below 1,500 meters, while balancing hospital grade (e.g. 10 Tier 2 and 20 Tier 3). Patients will be recruited in hospital outpatient setting, where all potentially eligible asthma patients will be consecutively approached and invited to join the study, e.g., regardless of new patients or treated, exacerbation or regular follow-up.

The QIP (i.e., GINA 2021 guideline education/training and implementation) will be delivered to pulmonologists and specialist nurses in participating hospitals at hospital level, including pulmonologist-targeted initial comprehensive education based on GINA 2021, guideline implementation performance assessment and feedback, reinforcement learning, along with multiple online and offline approaches serving as reminders and supportive tools to ensure consistent education and to facilitate the asthma management in daily clinical practice in accordance with GINA 2021 recommendation.

Immediately after last patient has been enrolled at each site, the study intervention will be initiated, i.e., the initial comprehensive training on GINA 2021 will be offered to pulmonologists and specialist nurses in this hospital. All successfully enrolled participating patients will be followed up for up to 48 weeks and return to recruiting hospital for study visits every 12 weeks. The total participating duration in this study for each participating patient will be approximately 60 weeks.

The study aims to bridge the gap between the recommendations from GINA 2021 and current clinical practice via an asthma QIP (including GINA guideline education/training and implementation).

4.2 Scientific Rationale for Study Design

CARE FOR ALL is designed to evaluate the possibility to change the clinical practice by a QIP, focusing on pulmonologist-targeted GINA2021 guideline training and multiple approaches to ensuing its implementation.

GINA 2021 recommends asthma patients to be assessed every 1 to 3 months during treatment initiation and every 3 months thereafter. Therefore, participating patients will be followed up every 12 weeks, with a total of 6 visits during the study period.

The primary endpoint is to evaluate an ICS-based maintenance and/or reliever treatment,

which is a direct measure of pulmonologist's behaviour on asthma treatment. The key secondary endpoint is to evaluate well-control asthma rate indicated by ACQ-5 ≤ 0.75 , which reflect the extent of patients' asthma symptom control. ACQ-5 is a numerical tool assessing asthma control recommended by GINA and widely used in clinical practice and research worldwide.

4.2.1 Participant Input into Design

Not applicable.

4.3 Justification for Dose

Not applicable.

4.4 End of Study Definition

A participant is considered to have completed the study if he/she has completed all phases of the study including the last visit.

The end of the study is defined as the date of the last visit of the last participating patient in the study shown in the Schedule of Activities.

5 STUDY POPULATION

Hospitals will be recruited according to the following selection criteria. The QIP will be delivered at hospital level to all pulmonologists and specialist nurses in the respiratory department.

5.1 Hospital Selection

Tier 2 and Tier 3 hospitals that meet all of the following criteria will be considered for inclusion in this study:

1. Public general hospitals (exclude Traditional Chinese Medicine hospitals)
2. The hospital has emergency unit, respiratory department, with corresponding wards and fundamental respiratory facilities, e.g., spirometry
3. Availability of guideline recommended treatment medicines in the hospital
4. At least 500 asthma patients visited the hospital in the past 1 year
5. Willing to give all the pulmonologists regular guideline education, diagnose and treat asthma patients according to the preferred approach according to the recommendation given by GINA 2021.

To represent the real world situation of patients, pulmonologists and treatment practice, hospital selection will include as many as provinces or municipalities in mainland China, where the altitude is below 1,500 meters, while balancing hospital grade (e.g. 10 Tier 2 and 20 Tier 3).

5.2 Patient Selection

Prospective approval of protocol deviations to recruitment and enrolment criteria, also known as protocol waivers or exemptions, is not permitted. Patient will be recruited in hospital outpatient setting and all potential eligible patients will be consecutively approached and invited to join the study, e.g., regardless of new patients or treated, exacerbation or regular follow-up, to avoid selection bias.

5.2.1 Patient Inclusion Criteria

Participants are eligible to be included in the study only if all of the following criteria apply:

1. Participant must be 14 years of age or older at the time of signing the informed consent.
2. Physician-confirmed asthma diagnosis with documented evidence of variable expiratory airflow limitation (e.g. from bronchodilator reversibility testing or other test)
3. Participating patients and/or their legally authorised representative must provide signed and dated written informed consent form prior to any study specific procedures.

5.2.2 Patient Exclusion Criteria

Patients are excluded from the study if any of the following criteria apply:

1. Previous diagnosis of chronic obstructive pulmonary disease (COPD) or other clinically relevant chronic respiratory disease other than asthma
2. Any significant disease or disorder (e.g. cardiovascular, pulmonary other than asthma, gastrointestinal, hepatic, renal, neurological, musculoskeletal, endocrine, metabolic, malignant, psychiatric, major physical impairment) which, in the opinion of the investigator, may either put the patient at risk because of participation in the study, or may influence the results of the study, or the patient's ability to participate in the study
3. Disease or condition other than asthma that requires treatment with systemic or oral steroids
4. Participation in another clinical study with an Investigational Product administered in the last 3 months prior to Visit 1.

5.3 Lifestyle Considerations

No lifestyle restrictions will be required in this study.

5.4 Screen Failures

Screen failures are defined as participants who consent to participate in the clinical study but are not subsequently entered in the study. These patients should have the reason as “Eligibility Criteria not Fulfilled”, i.e., patients do not meet the required inclusion/exclusion criteria.

[figure not shown]
A minimal set of screen failure information is required to ensure transparent reporting of screen failure participants to meet the Consolidated Standards of Reporting Trials (CONSORT) publishing requirements and to respond to queries from regulatory authorities. Minimal information that will be collected on the eCRF includes demography, screen failure details, eligibility criteria, and any serious adverse event (SAE).

6 STUDY INTERVENTION

6.1 Study Intervention – Quality Improvement Program

The intervention of Quality Improvement Program (i.e., GINA guideline education/training and implementation) will be delivered at the hospital level, targeting all pulmonologists and specialist nurses at participating hospitals, as illustrated in Figure 1. A scientific steering committee will be established and responsible for the overall quality and successful implementation of the QIP.

Figure 1 Study Design

The guideline education/training part includes pulmonologist-targeted GINA 2021 based initial comprehensive education and regular reinforcement learning (including but not limited to guideline training reinforcement, targeted education based on guideline implementation assessment and feedback, and case discussion). If GINA is updated, the updated content will also be delivered in educational interventions. The investigator information will be collected and analysed, including job category (doctor or nurse), age, years of work experience,

professional title, education background, assessment of inhaler skill score, etc.

The guideline implementation part focuses on regular assessment and feedback on guideline adherence performance in practice. The feedback will be used to guide QIP adjustment, e.g., reinforcement learning.

Multiple online and offline approaches serving as reminders and supportive tools to the QIP. The online approach will also facilitate pulmonologists and specialist nurses to manage their patients.

6.1.1 The Scientific Content of Guideline Education

The education content is based on GINA 2021 recommendations, including the following major components:

- Asthma disease knowledge
- Asthma diagnosis and assessment
- GINA 2021 recommended evidence-based asthma treatment, e.g., low-dose ICS-formoterol as preferred reliver and the scientific rationale. A GINA 2021 based treatment pathway will be suggested to be followed by participating pulmonologists.
- How to educate and manage patients, e.g., written action plan, shared goals development, rationale for medication adherence, difference between reliever and controller, prevention of symptoms and flare-ups, how to recognize worsening asthma and what actions to take, etc.

The scientific steering committee (see section 6.1.2.4) will ensure the education and training materials are scientifically and clinically appropriate and fit-for-purpose.

6.1.2 The Process of Intervention

The QIP includes pulmonologist-targeted guideline education and guideline implementation.

- Guideline education includes the initial comprehensive training and reinforcement learning. The initial comprehensive education will be delivered at each participating hospital by a dedicated qualified team, immediately after last patient enrolled at each site. The PI of respiratory departments from participating hospitals are responsible for arranging the delivery of hospital-level reinforcement learnings, multi-centres reinforcement training and so on. and ensuring the quality and success of hospital-level guideline implementation.
- The pulmonologists' guideline adherence and performance at participating hospitals will

be regularly assessed during the study period.

6.1.2.1 Fit-for-Purpose Pulmonologist-Targeted Education

Guideline education includes the initial comprehensive training and reinforcement learning. Pulmonologists and specialist nurses are required to attend these educations during the study period; and to apply the treatment pathway and patient management into daily clinical practice, in accordance with GINA recommendation, including educating their asthma patients, developing the written asthma action plan and timely interacting with patients.

1) Initial Comprehensive Training

Immediately after the completion of patient recruitment at each participating hospital, pulmonologists and specialist nurses will be requested to attend an initial interactive comprehensive training provided by a dedicated and qualified training team (section 6.1.2.5). A questionnaire about the awareness of asthma-related diagnosis and treatment will be conducted to all pulmonologists before the training. A training quiz will be conducted to ensure the successful delivery of the training. It is required that pulmonologists pass the Quiz (score 80 and above). Re-training and re-test will be performed to those pulmonologists who have not passed the Quiz.

After the initial comprehensive training, pulmonologists are encouraged to implement the asthma management in accordance with GINA recommendation in their routine clinical practice, including asthma patient assessment, treatment pathway, patient management, developing and reviewing written asthma action plan.

2) Reinforcement Learning

The hospital-level reinforcement learnings will be integrated into the regular department lectures. The PI of respiratory departments from participating hospitals are responsible for the delivery of hospital-level reinforcement learnings, and ensuring the quality and success of hospital-level guideline implementation.

During the study period, pulmonologists, especially those who will work at out-patient department in the upcoming 2 months, are required to attend the reinforcement learning, focusing on guideline training reinforcement, target learning based on feedback from the assessment of guideline implementation performance, and case discussion from clinical practice. The PI of the respiratory departments are responsible for arranging a platform to deliver the reinforcement learnings in case of worsening COVID-19 pandemic.

The frequency of the learning will be monthly in the first 3 months, and it can be decreased to bi-monthly or quarterly in the following study period, if the average proportion of each KPI checkpoint achievement (see section 6.1.2.3) of the respiratory department reaches 80% or

above and obtain the approval from scientific steering committee (see section 6.1.2.4).

For the common clinical issues in the GINA implementation by participating centers, training for all participating centers can be conducted every 3 months.

6.1.2.2 Multiple Online and Offline Approaches as Reminder and Support

Multiple approaches will be used to ensure consistent education and to facilitate the effective implementation of GINA 2021 in routine clinical practice.

1) Offline Approaches

- Clinic posters will be provided to illustrate the standard asthma diagnosis, assessment and recommended treatment algorithm included in the training materials, serving as a reminder to pulmonologists and specialist nurses during their clinical practice.
- Patient pamphlets will be provided to pulmonologists and/or specialist nurses to aid patient instruction, e.g. basic information on asthma disease and treatment, treatment compliance, inhaler technique, exacerbation identification in daily life. The content will be in plain language appropriate for laymen.

2) Online Approaches

An online platform through WeChat, a unit set-up independently during study period, will support the online approach for pulmonologist-targeted GINA guideline education and for facilitating the patients management by pulmonologists and/or specialist nurses.

- Pulmonologist-targeted GINA guideline education
 - The platform will be a repository for guideline training course and material.
 - The summary of reinforcement learning will be available as a reminder for those who attended and as a supplementary learning material for those who did not.
 - Frequent Asked Questions (FAQ) from Patients will be developed and kept up-to-dated during the study conduct, facilitating patient management by pulmonologists and/or specialist nurses.
- Facilitating the patient management by pulmonologists and/or specialist nurses. The patient management online approach will be a mini-program through WeChat, including but not limited to
 - A repository for patient education material, e.g. how to avoid environmental exposure, how to recognize worsening asthma and what actions to take, inhaler

technique video

- Patient self-management tool to facilitate physician timely evaluate the symptom control and risk factors
- A platform for the communication between pulmonologist and patients (e.g. questions and answers)

6.1.2.3 Guideline Implementation Performance Assessment with Feedback and Adjustment

Guideline implementation performance will be monthly assessed based on pre-defined key performance indicator (KPI).

The guideline implementation performance will be evaluated based on the following 6 checkpoints for each participating participant's visit.

1. Whether or not the pulmonologist or the specialist nurse has assessed the patient's symptom control over the past 4 weeks
2. Whether or not the pulmonologist or the specialist nurse has watched the patient using their inhaler and educate the technique
3. Whether or not the pulmonologist has a discussion about treatment adherence
4. Whether or not the pulmonologist has developed or reviewed the written asthma action plan
5. Whether or not the pulmonologist has reduced the dosage of asthma treatment? If yes, whether or not the patient had a PFT before dosage reduction?
6. Whether or not the pulmonologist has provided the treatment with ICS-containing medication

During the study, the first 5 questions will be evaluated by participating patients with a questionnaire after his/her visit to the pulmonologist(include nurses). The last question will be checked based on the treatment options.

The proportion of each checkpoint achievement will be calculated at department level. identifying where the improvement and the issue might be, to facilitate the future education/training more targeted. The criteria of KPIs will be reviewed by the scientific steering committee (see section 6.1.2.4).

The regular feedback on hospital-level guideline implementation performance will be

provided to The PI of respiratory departments and national principal investigators. If the guideline implementation performance is not satisfying, the scientific steering committee will lead the discussion with the director of respiratory department on root cause analyses, and provide guidance/instruction for improvement plan.

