1.3 Schedule of Activities

Table 1 Schedule of Activities (participating patients related)

Study Visit	Baseline Period	Intervention Period					Details in CSP Section or Appendix
		V1	V2	V3	V4	V5 (Study completion/ withdrawal)	
Weeks	V0	-12 ± 7	0 ± 14	12 ± 7	24 ± 7	36 ± 7	48 ± 7
Informed consent ^a	X						
Inclusion and exclusion criteria	X						Sections 5.2.1 and 5.2.2. 2
Demographics ^b	X						
Vital Sign ^c	X						
Subject status ^d	X						
Smoking status ^e	X						
Medical history (comorbidities) and medications ^f	X						
Asthma history & related treatment ^g	X						
Severe asthma exacerbation		X	X	X	X	X	
Hospitalization due to asthma exacerbation since last visit		X	X	X	X	X	Section 8.1.4
ACQ-5	X	X	X	X	X	X	Section 8.1.5.1
AQLQ(S)+12	X	X	X	X	X	X	Section 8.1.5.2
PFT	X					X	
MARS-A questionnaire	X		X	X		X	
Questionnaire of asthma knowledge for patient	X		X	X		X	
Inhale skill score for patient		X	X	X		X	

Study Visit	Baseline Period	Intervention Period					Details in CSP Section or Appendix
		V1	V2	V3	V4	V5 (Study completion/ withdrawal)	
Patient's expectation for asthma treatment	X		X	X		X	
Laboratory assessments within prior 3 months (if available in medical records) ^h	X	X	X	X	X	X	
PFT/BPT/PEF/FeNO within prior 3 months (if available in medical records)	X	X	X	X	X	X	
Medical records on asthma related assessment and treatment	X	X	X	X	X	X	
Questionnaire for Asthma Patients during COVID-19 ⁱ	X						Section 8.1.9
Patient evaluation on whose pulmonologists 1. assess symptom control, 2. watch the patient using their inhaler, educate their technique, 3. have a discussion about adherence, 4. develop or review the written asthma action plan, provide patient education, 5. had a PFT before dosage reduction	X	X	X	X	X	X	Section 6.1.2.3

PFT = Pulmonary Function Testing; BPT = Bronchial provocation test; PEF = Peak expiratory flow; FeNO = Fractional exhaled nitric oxide

- a. Informed consent must be conducted prior to performing any study procedures including data collection.
- b. Demographic includes patient age, gender, race, ethnicity and
- c. Vital signs include body mass index (BMI, calculation by height and weight)
- d. Subject Status education level, family monthly income, job, residence (urban communities or rural villages), etc
- e. Smoking status include current smoker or stopping smoking or restarting smoking, smoking pack-years

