8.1.6.3 Patient Evaluation on Guideline Implementation KPIs

Guideline implementation performance will be assessed based on pre-defined key performance indicator (KPI). After seeing their pulmonologists, participating patients will be asked the following 5 KPI questions:

- Whether or not your pulmonologist or specialist nurse has assessed your symptom control over the past 4 weeks?
- Whether or not your pulmonologist or specialist nurse has watched you using your inhaler and educate the technique?
- Whether or not your pulmonologist has a discussion about why you need a long-term medication adherence?
- Whether or not your pulmonologist has developed or reviewed the written asthma action plan?
- Whether or not the pulmonologist has reduced the dosage of asthma treatment? If yes, whether or not you had a PFT before dosage reduction?

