8.1.8 Inhaler skill score assessment

Regarding the technical standards of inhalation, there are relevant regulations in national guidelines, and the overall process is consistent ([Chinese expert consensus on standard application of inhalation device in stable chronic airway disease patients, 2019](#)). Regarding the technical standards of inhalation, there are relevant regulations in national guidelines, and

the overall process is consistent (Chinese expert consensus on standard application of inhalation device in stable chronic airway disease patients, 2019). The study is designed for 7 steps, with 1 point for each step, and the full score is 7 points. The technical evaluation of inhaler is based on devices which commonly used by researchers participating in the study. Inhaler skill shall be assessed by the group from leading site before and after education, and the subjects shall be instructed only after investigators pass this assessment. Random inspections will be conducted during the follow-up period. V1 allows the subjects to demonstrate the inhalation process such as the dosing or the using method with the prepared device, and the researcher controls the operating standard as the baseline. It is recommended that each centre recommend 1-2 physicians or nurses, who are trained and qualified to be responsible for this work, and adopt uniform standards. (Appendix E)

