5 INTERIM ANALYSIS

There will be two interim analyses, first interim analyses will mainly focus on the baseline when all subjects enrolled and finish baseline assessment, and the other will happen when all subjects complete week 12 visit.

First interim analysis includes the following parts:

1. Subject disposition
2. Demographics
3. Substance use – nicotine
4. Asthma history
5. Historical asthma exacerbation
6. Prior and concomitant medications – asthma/asthma related comorbidities
7. Prescribed medication – asthma
8. ICS-based maintenance and/or reliever treatment
9. ACQ-5 average scores
10. Distribution of ACQ-5 average scores (Well controlled/Partly controlled/Not well-controlled) and its subgroup listed in Section 4.2.3.12
11. ICS-formoterol as reliever
12. Asthma treatment patterns
13. Numbers of severe asthma exacerbation
 - a. With ICS containing vs. without ICS containing
 - b. Good adherence vs. not
14. Health-related quality of life evaluated by Asthma Quality of Life Questionnaire for 12 years and older (AQLQ(S)+12) score
15. MARS-A average score
16. Hematology

17. Blood Gas
18. IgE
19. FeNO
20. Pulmonary Function Test (PFT)
21. Pulmonary Function Test-Post-BDT (PFT)

Second interim analysis includes the following parts:

1. Subject disposition
2. Demographics
3. Substance use – nicotine
4. Asthma history
5. Historical asthma exacerbation
6. Prior and concomitant medications – asthma/asthma related comorbidities
7. Prescribed medication – asthma
8. ICS-based maintenance and/or reliever treatment
9. ACQ-5 average scores
10. Distribution of ACQ-5 average scores (Well controlled/Partly controlled/Not well-controlled) and its subgroup listed in Section 4.2.3.12
11. ICS-formoterol as reliever
12. Asthma treatment patterns
13. Patient evaluation on whose pulmonologists (whether their pulmonologists develop or review the written asthma action plan and watch the patient using their inhaler, checking their technique)
14. Numbers of severe asthma exacerbation
 - a. With ICS containing vs. without ICS containing
 - b. Good adherence vs. not

15. Health-related quality of life evaluated by Asthma Quality of Life Questionnaire for 12 years and older (AQLQ(S)+12) score
16. MARS-A average score
17. Inhaler skill score of subjects
18. Asthma knowledge score of subjects
19. Patient expectations of asthma treatment
20. Asthma knowledge questionnaire score of investigators
21. Adverse event
22. Hematology
23. IgE
24. FeNO
25. Pulmonary Function Test (PFT)

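### Study inhaler skill scoring may inflate KPI checkpoint 2 at the visits where it is done, so a change in that checkpoint cannot be read as a change in practice alone

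*Protocol*

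**What the plan says.** **The checkpoint.** Protocol 6.1.2.3 lists six checkpoints. The second is "Whether or not the pulmonologist or the specialist nurse has watched the patient using their inhaler and educate the technique". On who answers, the section says that "the first 5 questions will be evaluated by participating patients with a questionnaire after his/her visit to the pulmonologist(include nurses". Protocol 8.1.6.3 gives the patient's wording: "Whether or not your pulmonologist or specialist nurse has watched you using your inhaler and educate the technique". In the protocol's Schedule of Activities (1.3), the row containing "watch the patient using their inhaler, educate their technique" is marked at all six visits, V0 to V5.

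**The study scoring.** Protocol 8.1.8 has patients demonstrate inhaler use while staff check it against a seven-step standard. It provides for patients to be instructed once staff have passed their own assessment. On who scores: "It is recommended that each centre recommend 1-2 physicians or nurses, who are trained and qualified to be responsible for this work". The Schedule of Activities row "Inhale skill score for patient" is marked at V1, V2, V3 and V5 and is blank at V0 and V4. The corresponding row in SAP 1.2, Table 1 shows the same pattern.

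**Where the schedule is contradicted.** Protocol section 8 lists the skill score among the V0 data, and describes it for follow-up visits V1 to V5 with no exception for V4. The synopsis (1.1, Data Collection and Management) also gives V1 to V5. Section 8.1.8 treats V1 as the skill-score baseline, which fits the blank at V0.

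**How the checkpoint is used.** Under Protocol 6.1.2.1, reinforcement learning is monthly for the first 3 months. It may then become less frequent "if the average proportion of each KPI checkpoint achievement (see section 6.1.2.3) of the respiratory department reaches 80% or" above, with steering committee approval. SAP section 5 includes the item ("watch the patient using their inhaler, checking their technique") in the second interim analysis.

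**The concern.** The checkpoint is meant to show whether clinicians changed what they do in the consultation. At a scored visit, a physician or nurse observes the patient's technique because the study requires it, and may also instruct the patient. A patient asked afterwards can truthfully say yes on that basis. Nothing in the visible text tells patients to set the scoring aside, or fixes whether the KPI questionnaire comes before or after it.

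Under the Schedule of Activities, the item is asked at two visits without scoring and four with it. Part of any rise from V0 to V1 or V2, and of any fall from V3 to V4, could then come from the visit schedule.

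Two uses are at stake. The second interim analysis, after the week 12 visit, names this item. The 80% rule for less frequent training also takes it as one input, and the scheduled KPI visits over the first 3 months after training (V1 and V2) both carry scoring. Protocol 6.7 discusses the Hawthorne effect in general terms but not this overlap.

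**Working it through.** The plan states no figure for this point, so there is none to reproduce. The check sets the two schedules side by side and then sizes the possible shift under assumed values.

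**Step 1: schedules**

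| Visit | KPI item asked (1.3) | Scoring, Schedule of Activities | Scoring, section 8 text |
|---|---|---|---|
| V0 | yes | no | yes |
| V1 | yes | yes | yes |
| V2 | yes | yes | yes |
| V3 | yes | yes | yes |
| V4 | yes | no | yes (no exception stated) |
| V5 | yes | yes | yes |

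**Step 2: model.** Let q be the routine-care rate, and s the share of the remaining patients who answer yes because of the scoring. Both are assumptions. The reported rate is q at an unscored visit and q + (1 - q)s at a scored visit. With q constant, the spurious difference is (1 - q)s.

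**Step 3: size under the Schedule of Activities**

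| q | s = 0 | s = 25% | s = 50% | s = 100% |
|---|---|---|---|---|
| 30% | 0 | 0.70 × 0.25 = 17.5 points | 0.70 × 0.50 = 35 points | 70 points |
| 40% | 0 | 15 points | 30 points | 60 points |
| 60% | 0 | 10 points | 20 points | 40 points |

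Over q from 20% to 80% and s from 0 to 100%, the range is 0 to 80 points. At q = 60% and s = 50%, the reported rate at scored visits is 60 + 20 = 80%, with no change in practice.

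**Step 4: the 80% rule.** If the rule means the average of the six checkpoints (the text is ambiguous), the shift in that average is (1 - q)s/6. At q = 30% this is 17.5/6 = 2.9 points at s = 25% and 70/6 = 11.7 points at s = 100%. Without inflation, the other five checkpoints must average (6 × 80 - 30)/5 = 90% to reach 80%. With s = 25% they need (480 - 47.5)/5 = 86.5%; with s = 100% they need (480 - 100)/5 = 76%. So at q = 30% the scoring changes the outcome only if the other five average between 86.5% and 90% (s = 25%), or between 76% and 90% (s = 100%).

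**Step 5: scoring at every visit, as section 8 reads.** If the true rate moves from q1 to q2, the observed change is [q2 + (1 - q2)s] - [q1 + (1 - q1)s] = (q2 - q1)(1 - s). The spurious rise is zero when practice is constant, but each level is still raised. For example, a true move from 30% to 50% with s = 50% is reported as 65% to 75%: 10 points instead of 20.

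**The case against.** A reader might infer that scoring automatically fulfils checkpoint 2, so that it must rise after baseline and dip at V4. The documents do not support that, for four reasons:

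- The item needs both observation and teaching. It asks about the patient's own inhaler and clinician, whereas 8.1.8 describes a demonstration at V1 with a prepared device, and recommends designated scorers who need not be the treating clinician. Nothing says that scoring counts as achievement.
- Staff may watch technique in routine care at V0 and V4, and the training may truly raise the rate.
- The blanks at V0 and V4 are contradicted by section 8 and, for V4, by the synopsis.
- The size depends wholly on s, which could be zero.

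These points remove any claim of a certain or minimum artefact. They do not remove the possibility: 8.1.8 also provides for instruction, the scorers can be the kinds of staff the item names, and the questionnaire does not separate the two settings.

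A reader might also infer that training could be cut back on the strength of scoring alone. That goes too far. Committee approval is required, the committee reviews the KPI criteria, and performance is assessed monthly and by patient visit, so V1 and V2 need not be the only inputs. Nor can one say that the SAP lacks an exclusion: the exploratory endpoint text is not visible.

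Finally, if a nurse watches and teaches the patient during scoring, that is arguably the care the programme wants. As a measure of changed practice, however, it should be distinguishable from a scheduled study task.

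**Conclusion.** The point holds as a possible measurement bias of unknown size. Under the Schedule of Activities, checkpoint 2 may be raised at V1, V2, V3 and V5 relative to V0 and V4 by (1 - q)s. If scoring is done at every visit, comparisons over time lose the spurious rise, but levels are too high and true gains are shrunk by the factor (1 - s). For any s above zero, checkpoint 2 does not cleanly measure consultation practice under either schedule.

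This rests on three assumptions: some patients count the scoring when they answer, q and s take values the documents do not give, and no unseen text tells patients to exclude the scoring. The consequences are confined to an interim output and one input to the training-frequency rule. The primary and secondary endpoints are unaffected.

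**What to change.** 1. Reconcile the synopsis, the Schedule of Activities, section 8 and section 8.1.8 on the visits at which skill scoring is done.
2. In 8.1.6.3 and on the KPI form, have patients answer the KPI questions after the consultation and before any skill scoring. Add *not counting the study inhaler skill scoring* to question 2. This works under either schedule.
3. For data already collected, keep all visits, flag those where scoring was done, and state that changes in checkpoint 2 between scored and unscored visits may reflect the study procedure. Show V0 versus V4 only as a supplementary comparison, and only if the data confirm that neither visit was scored.

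Restricting the report to V0 and V4, or dropping checkpoint 2 from the 80% rule at the scored visits, is not recommended: it would discard data on the strength of a disputed schedule.

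The cost is a form change, an instruction on visit order and a sentence in the SAP. Checkpoint 2 rates may look less favourable.
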